### 5.2.6.3.1 Management of Hypertension

Hypertension is a recognized side effect of treatment with drugs inhibiting VEGF signaling. Investigators should therefore ensure that subjects enrolled to receive treatment with lenvatinib have BP of  $\leq 150/90$  mm Hg at the time of study entry and, if known to be hypertensive, have been on a stable dose of antihypertensive therapy for at least 1 week before C1D1. Early detection and effective management of hypertension are important to minimize the need for lenvatinib dose interruptions and reductions.

Regular assessment of BP should be as detailed in the SoA (Section 6.3). Hypertension will be graded using NCI CTCAE v4.0, based on BP measurements only (and not on the number of antihypertensive medications).

If the subject's first BP measurement of the current assessment is elevated (ie, systolic BP  $\geq 140$  mm Hg or diastolic BP  $\geq 90$  mm Hg), the BP measurement should be repeated at least 5 minutes later. One BP assessment is defined as the mean value of 2 measurements at least 5 minutes apart. If the BP assessment (ie, the mean of the 2 BP measurements obtained at least 5 minutes apart) is elevated (systolic BP  $\geq 140$  mm Hg or diastolic BP  $\geq 90$  mm Hg), a confirmatory assessment should be obtained at least 30 minutes later by performing 2 measurements (at least 5 minutes apart) to yield a mean value.

Antihypertensive agents should be started as soon as elevated BP (systolic BP  $\geq 140$  mm Hg or diastolic BP  $\geq 90$  mm Hg) is confirmed on 2 assessments at least 30 minutes apart. The choice of antihypertensive treatment should be individualized to the subject's clinical

circumstances and follow standard medical practice. For previously normotensive subjects, appropriate antihypertensive therapy should be started when systolic BP  $\geq 140$  mm Hg or diastolic BP  $\geq 90$  mm Hg is first observed on 2 assessments at least 30 minutes apart. For those subjects already on antihypertensive medication, treatment modification may be necessary if hypertension persists.

Lenvatinib should be withheld in any instance where a subject is at imminent risk to develop a hypertensive crisis or has uncontrolled hypertension (eg, BP  $\geq 160/100$  mm Hg) with significant risk factors for severe complications, significant risk factors for cardiac disease, intracerebral hemorrhage, or other significant co-morbidities. Once the subject has been on the same antihypertensive medications for at least 48 hours and the BP is controlled, lenvatinib should be resumed as described below.

Subjects who have had systolic BP  $\geq 160$  mm Hg or diastolic BP  $\geq 100$  mm Hg must have their BP monitored on Day 15 (or more frequently as clinically indicated) until systolic BP has been  $\leq 150$  mm Hg and diastolic BP has been  $\leq 95$  mm Hg for 2 consecutive treatment cycles. If a repeat event of systolic BP  $\geq 160$  mm Hg or diastolic BP  $\geq 100$  mm Hg occurs, the subject must resume the Day 15 evaluation until systolic BP has been  $\leq 150$  mm Hg and diastolic BP has been  $\leq 95$  mm Hg for 2 consecutive treatment cycles. A diary will be provided to the subject to capture the blood pressure evaluations between study visits.

The following guidelines should be followed for the management of systolic BP  $\geq 160$  mm Hg or diastolic BP  $\geq 100$  mm Hg confirmed on 2 BP assessments at least 30 minutes:

1. Continue study drug and institute antihypertensive therapy for subjects not already receiving this.
2. For those subjects already on antihypertensive medication, the dose of the current agent may be increased, if appropriate, or 1 or more agents of a different class of antihypertensive should be added. Study treatment can be continued without dose modification.
3. If systolic BP  $\geq 160$  mm Hg or diastolic BP  $\geq 100$  mm Hg persists despite maximal antihypertensive therapy, then lenvatinib administration should be interrupted and restarted at 1 dose level reduction only when systolic BP  $\leq 150$  mm Hg and diastolic BP  $\leq 95$  mm Hg and the subject has been on a stable dose of antihypertensive medication for at least 48 hours.
  - If systolic BP  $\geq 160$  mm Hg or diastolic BP  $\geq 100$  mm Hg recurs on the first dose reduction despite optimal management of hypertension with antihypertensive medications (either by dose increase or the addition of a different class of antihypertensive), then lenvatinib administration should be interrupted and restarted at an additional dose reduction only when systolic BP  $\leq 150$  mm Hg and diastolic BP  $\leq 95$  mm Hg and the subject has been on a stable dose of antihypertensive medication for at least 48 hours.
  - If systolic BP  $\geq 160$  mm Hg or diastolic BP  $\geq 100$  mm Hg recurs on the second dose reduction despite optimal management of hypertension with antihypertensive medications (either by dose increase or the addition of a different class of antihypertensive), then lenvatinib administration should be

interrupted and restarted at a third dose reduction only when systolic BP  $\leq$ 150 mm Hg and diastolic BP  $\leq$ 95 mm Hg and the subject has been on a stable dose of antihypertensive medication for at least 48 hours.

- Additional dose reduction should be discussed with the Sponsor.

The following guidelines should be followed for the management of Grade 4 hypertension (life threatening consequences):

1. Institute appropriate medical management
2. Discontinue study drug

### **5.2.6.3.2 Management of Proteinuria**

Regular assessment of proteinuria should be conducted as detailed in the SoA (Section 6.3). Guidelines for assessment and management of proteinuria are as follows:

#### **Detection and Confirmation**

1. Perform urine dipstick testing or urinalysis per the SoA (Section 6.3). Urine dipstick testing is the preferred method for testing for urinary protein, however, urinalysis may be used if the use of urine dipsticks is not feasible.
2. A 24-hour urine collection initiated as soon as possible and at least within 72 hours (or an immediate spot urine protein-to-creatinine ratio [UPCR] test) is required in the following situations:
  - The first (initial) occurrence of  $\geq$ 2+ ( $\geq$ 100 mg/dL) proteinuria on urine dipstick (or urinalysis) while the subject is receiving lenvatinib.
  - A subsequent increase in severity of urine dipstick or urinalysis proteinuria occurring on the same lenvatinib dose level.
  - When there has been a lenvatinib dose reduction and at the new dose level the urine protein dipstick result is  $\geq$ 2+ ( $\geq$ 100 mg/dL).
3. A 24-hour urine collection (initiated as soon as possible and at least within 72 hours) to verify the grade of proteinuria is required when UPCR is  $\geq$ 2.4.

#### **Grading of Proteinuria**

- Grading according to NCI CTCAE v4.0 will be based on the 24-hour urinary protein result if one has been obtained. If the participant has 4+ proteinuria by dipstick ( $\geq$ 1000 mg/dL by urinalysis), a 24-hour urinary protein result is required to confirm Grade 3 proteinuria. Management of lenvatinib administration will be based on the grade of proteinuria according to [Table 7](#).

#### **Monitoring**

- Urine dipstick or urinalysis testing for subjects with proteinuria  $\geq$ 2+ ( $\geq$ 100 mg/dL) should be performed on Day 15 (or more frequently as clinically indicated) until the results have been 1+ (30 mg/dL) or negative for 2 consecutive treatment cycles.

- Proteinuria monitoring can be performed at the local laboratory or investigator site, but must be managed by the site physician.
- In the event of nephrotic syndrome, lenvatinib must be discontinued.

#### **5.2.6.3.3 Management of Diarrhea**

An anti-diarrheal agent should be recommended to the subject at the start of study treatment, and subjects should be instructed and educated to initiate anti-diarrheal treatment at the first onset of soft bowel movements. The choice of anti-diarrheal agent should be individualized to the subject's clinical circumstances and follow standard medical practice. If signs/symptoms of diarrhea persist despite optimal medical management, instructions contained in [Table 7](#) should be followed.

#### **5.2.6.3.4 Management of Hepatotoxicity**

Liver function tests (alanine transaminase [ALT], aspartate transaminase [AST], bilirubin levels) should be conducted as detailed in the SoA (Section 6.3) and as clinically indicated. If signs/symptoms indicating liver injury occur, instructions contained in [Table 7](#) should be followed. Appropriate supportive care should be provided together with close monitoring. If hepatic failure (any grade per CTCAE v4.0) occurs, the study drug must be discontinued.

#### **5.2.6.3.5 Management of Thromboembolic Events**

Subjects should be advised to pay attention to symptoms suggestive of venous thromboembolic events which include acute onset of shortness of breath, dyspnea, chest pain, cough, hemoptysis, tachypnea, tachycardia, cyanosis, DVT signs including lower-extremity swelling, and warmth to touch or tenderness. In case any of these symptoms appear, subjects should be instructed to report such symptoms promptly to the treating physician. If a thromboembolic event is confirmed, instructions contained in [Table 7](#) should be followed. Appropriate supportive care should be provided together with close monitoring. If a subject experiences a Grade 3 or a life threatening (Grade 4) thromboembolic reaction, including pulmonary embolism, lenvatinib must be discontinued.

Arterial thromboembolic events (eg, new onset, worsening, or unstable angina, myocardial infarction, transient ischemic attack, and cerebrovascular accident) of any grade require study treatment discontinuation.

#### **5.2.6.3.6 Management of Posterior Reversible Encephalopathy Syndrome/Reversible Encephalopathy Syndrome/ Reversible Posterior Leukoencephalopathy Syndrome**

Posterior Reversible Encephalopathy Syndrome/Reversible Encephalopathy Syndrome/ Reversible Posterior Leukoencephalopathy Syndrome (PRES/RPLS) is a neurological disorder that can present with headache, seizure, lethargy, confusion, altered mental function, blindness, and other visual or neurological disturbances. Mild to severe hypertension may be present. MRI is necessary to confirm the diagnosis of PRES/RPLS. Appropriate measures should be taken to control BP. In subjects with signs or symptoms of PRES/RPLS, instructions in [Table 7](#) should be followed.

### 5.2.6.3.7 Management of Hypocalcemia

Serum calcium should be monitored per the SoA (Section 6.3). Corrected serum calcium should be used to assess the grade of hypocalcemia per CTCAE v4.0, using the following formula:

$$\text{Corrected calcium} = ([4 - \text{serum albumin in g/dL}] \times 0.8 + \text{serum calcium})$$

The formula is not applicable when serum albumin concentration is normal ( $>4$  g/dL); in such situations, the total (uncorrected) serum calcium should be used instead.

Hypocalcemia should be treated per institutional guidelines (eg, using appropriate calcium, magnesium, and Vitamin D supplementation) until resolution.

### 5.2.6.3.8 Management of Hemorrhage

Instructions in [Table 7](#) should be followed for the management of hemorrhage. Either resume at a reduced dose or discontinue lenvatinib depending on the severity and persistence of hemorrhage.

### 5.2.6.3.9 Management of Gastrointestinal Perforation or Fistula Formation

Lenvatinib should be discontinued in any subjects who develop gastrointestinal perforation of any grade or Grade 4 fistula.

### 5.2.6.3.10 Management of QT Prolongation

Lenvatinib should be withheld in the event of development of QT interval prolongation greater than 500 msec. Lenvatinib should be resumed at a reduced dose when QTc prolongation is resolved to  $<480$  msec or baseline. Monitor potassium, calcium and magnesium, and replenish as appropriate.

### 5.2.6.3.11 Management of Osteonecrosis of the Jaw

Perform an oral examination prior to treatment with lenvatinib and periodically during lenvatinib treatment. Advise participants regarding good oral hygiene practices. Avoid invasive dental procedures, if possible, while on lenvatinib treatment, particularly in participants at higher risk. For participants requiring invasive dental procedures, discontinuation of bisphosphonate treatment may reduce the risk of ONJ. Withhold lenvatinib if ONJ develops and restart based on clinical judgement of adequate resolution (See Section 5.2.6.5).

All study-related medical or dental decisions must be made by an investigator who is a qualified physician.

### 5.2.6.4 Dose Modifications for Overlapping Toxicities

Based on the known toxicity profiles of pembrolizumab, MK-4280, and lenvatinib, certain treatment-related AEs are uniquely associated with one drug versus the other. For example, hypertension, arterial thrombotic events, proteinuria, and hemorrhagic events are known risks for lenvatinib treatment, while immune-related AEs are risks for pembrolizumab and MK-

4280 treatment. However, certain AEs, such as such as diarrhea, hypothyroidism, and liver enzyme elevation, may be initially considered attributable to any study drug. Therefore, evaluation of attribution is important for determining the study drug most likely related to the AE, or an alternative etiology, and subsequently proper clinical management. The following aspects should be considered:

1. Timing of AE onset

Since lenvatinib is dosed daily and continuously due to a relatively short half-life (28 hours), and pembrolizumab is dosed Q3W due to a long half-life, lenvatinib can be interrupted to assess whether an AE improves/resolves with dechallenge (ie, interruption of treatment) based on the following two scenarios:

- If an AE is identified during a treatment cycle (ie, between 2 pembrolizumab doses), only lenvatinib dose interruption is needed.
- If an AE is identified at the beginning of a treatment cycle, lenvatinib can be interrupted and dosing of pembrolizumab should be held.

If the subject recovers from an AE in response to lenvatinib interruption (ie, positive dechallenge), the event is more likely to be related to lenvatinib. Otherwise, after excluding other alternative explanations, an immune-related AE should be considered.

2. Severity of AE

If an AE is suspected to be treatment related and is severe/life threatening at the time of onset or is rapidly worsened, action including interrupting all drugs and initiating treatment with a corticosteroid (with exception of hypothyroidism, TIDM) and other supportive care should be taken promptly.

3. Subjects receiving the combination therapy (pembrolizumab + MK-4280 + lenvatinib) must discontinue study therapy if any of the following occur:

- ALT or AST >5 X ULN for more than 2 weeks.

Pembrolizumab and MK-4280 will have already been permanently discontinued per [Table 5](#), but lenvatinib may be administered at a reduced dose by the time this criterion is met and must be permanently discontinued immediately.

- ALT or AST >3 X ULN and (TBL >2 X ULN or INR >1.5).

Although [Table 5](#) advises pembrolizumab and MK-4280 to be withheld (interrupted), and [Table 7](#) advises lenvatinib to have no dose modification or a reduction, if this criterion is met, all drugs must be permanently discontinued immediately.

### **5.2.6.5 Other Allowed Dose Interruptions**

If the subject is receiving treatment with lenvatinib and requires surgery during the study, the stop time and restart time of lenvatinib should be as follows:

- For minor procedures: stop lenvatinib at least 2 days before the procedure and restart it at least 2 days after, once there is evidence of adequate healing and no risk of bleeding.
- For major procedures: stop lenvatinib at least 1 week (5 half-lives) prior to surgery and then restart it at least 2 weeks after, once there is evidence of adequate healing and no risk of bleeding.
- For scheduled dental surgery or invasive dental procedures, stop lenvatinib for at least 1 week before the procedure, then restart lenvatinib when deemed clinically appropriate.

### **5.2.7 Crossover Criteria**

After Sponsor consultation, subjects in Arm 1 of Part B may be allowed to crossover to Arm 2C and receive MK-4280 in combination with pembrolizumab. In order to be eligible for crossover, the subject must have radiographically documented and confirmed disease progression per irRECIST 1.1 while in Arm 1. Subjects who discontinue treatment in Arm 1 for any reason other than disease progression are not eligible for crossover.

If crossover is being considered, the risks and benefits of continuing treatment after disease progression should be reviewed prior to performing any crossover-related procedures. Subjects will continue receiving MK-4280 at the dose-level they were assigned (ie, 800 mg), and pembrolizumab will be administered at the fixed 200 mg Q3W dose. Crossover will not be permitted until six subjects have completed the DLT period on Arm 2C. The subject may receive up to a total of 35 cycles of combination treatment (irrespective of how many cycles of monotherapy treatment they received).

Specific procedures to be performed for crossover subjects can be found in Section 6.3 – Crossover Flow Chart. Special considerations regarding imaging and disease assessment for crossover subjects can be found in Section 7.1.2.6 – Disease Assessments.

### **5.2.8 Second Course of Study Treatment**

All participants who have completed the first course may be eligible for up to an additional 17 cycles of study treatment if there is investigator-determined progressive disease after initial treatment has been completed. This retreatment is the Second Course of this study.

Note: Sponsor consultation is required prior to starting participants on Second Course.

Participants may enter the Second Course if all of the following criteria are met:

1. No new anticancer treatment was administered after the last dose of study intervention
2. The participant meets all of the inclusion criteria and none of the exclusion criteria
3. The study is ongoing

For participants in Arm 3, Arm 4 and Arm 6, continuation or resumption of the same concomitant therapy received during the initial treatment phase (ie, chemotherapy or lenvatinib) may be administered with Second Course MK-4280 and Pembrolizumab at the discretion of the Investigator. Note that chemotherapy or agent other than lenvatinib that is different from that received in the initial treatment phase is not permitted

### **5.2.9 Trial Blinding**

This is an open-label trial; therefore, the Sponsor, investigator and subject will know the treatment administered.

## **5.3 Randomization or Treatment Allocation**

Treatment allocation by nonrandom, sequential assignment to Part A, Arm 1 or Arm 2 will occur centrally using an IVRS/IWRS. Randomization for Cohort E in Part B will be performed at a 1:1 ratio by an IVRS/IWRS. An IVRS/IWRS will be used to control the sequential enrollment of Part B. Enrollment to Arm 3 or Arm 4 will be guided by a subject's eligibility for one arm or the other or, if eligible for both arms, will be determined by investigator choice. If Arms 1, 2C and 5 for 3L+ CRC subjects are enrolling at the same time, subjects will be assigned in an alternating fashion across the open arms at the study level through IVRS. Cohort F of Part B is only open to sites in China and these subjects will be assigned to Arm 5 only.

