#### 3.1 Primary Objective(s) & Hypothesis(es)

[figure not shown]
- 1) **Objective:** To determine the safety and tolerability of MK-4280 monotherapy (for subjects in Part A, Arm 1 and Part B, Arm 1) and to establish a maximum tolerated dose (MTD) or maximum administered dose (MAD)
- 2) **Objective:** To determine the safety and tolerability of MK-4280 in combination with pembrolizumab (for subjects in Part A, Arm 2 and Part B, Arm 2A, 2B and 2C) and to establish a preliminary recommended Phase 2 dose (RP2D) for combination therapy
- 3) **Objective:** To determine the safety and tolerability and to establish a preliminary RP2D of MK-4280 in combination with pembrolizumab and mFOLFOX7 (Arm 3) and of MK-4280 in combination with pembrolizumab and FOLFIRI (Arm 4) in subjects with MSS PD-1-treatment-naïve CRC that have received  $\leq 1$  line of prior therapy (Cohort B)
- 4) **Objective:** To determine the safety and tolerability of MK-4280 and pembrolizumab when administered as a co-formulated product (MK-4280A, Arm 5) and compare to the safety and tolerability of MK-4280 and pembrolizumab when administered sequentially (Part B subjects receiving MK-4280 800 mg plus pembrolizumab 200 mg Q3W, Arm 2C) (Cohort A)
- 5) **Objective:** To determine the safety and tolerability of MK-4280 and pembrolizumab when administered as a co-formulated product in subjects in China (MK-4280A, Arm 5, Cohort F)
- 6) **Objective:** To determine the safety and tolerability and to establish a preliminary RP2D of MK-4280 in combination with pembrolizumab and lenvatinib (Arm 6) in subjects with MSS PD-1-treatment-naïve CRC that have received 2 lines of prior therapy (Cohort G)

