#### 3.2 Secondary Objective(s) & Hypothesis(es)

[figure not shown]
- 1) **Objective:** To characterize the pharmacokinetic (PK) profile of MK-4280 in all subjects receiving MK-4280 alone, in combination with pembrolizumab, in combination with pembrolizumab and mFOLFOX7, in combination with pembrolizumab and FOLFIRI, and in combination with pembrolizumab and lenvatinib.

- 2) **Objective:** To characterize the PK profile of pembrolizumab in all subjects receiving pembrolizumab in combination with MK-4280 with or without mFOLFOX7, FOLFIRI, or lenvatinib
- 3) **Objective:** To characterize the PK profile of lenvatinib in subjects receiving lenvatinib in combination with MK-4280 and pembrolizumab
- 4) **Objective:** To evaluate the objective response rate (ORR) as determined by RECIST 1.1 as assessed by investigator review of MK-4280 alone and in combination with pembrolizumab for each tumor cohort in Part B separately
- 5) **Objective:** To evaluate the ORR as determined by RECIST 1.1 as assessed by investigator review of 2 doses of MK-4280 in combination with pembrolizumab for subjects with gastric cancer (Cohort E)
- 6) **Objective:** To evaluate the ORR as determined by RECIST 1.1 as assessed by investigator review of MK-4280 in combination with pembrolizumab and mFOLFOX7, and in combination with pembrolizumab and FOLFIRI in subjects with MSS PD-1-treatment-naïve CRC that have received  $\leq 1$  line of prior therapy (Cohort B)
- 7) **Objective:** To evaluate the ORR as determined by RECIST 1.1 as assessed by investigator review of MK-4280 in combination with pembrolizumab and lenvatinib in subjects with MSS PD-1-treatment-naïve CRC that have received 2 lines of prior therapy (Cohort G)
- 8) **Objective:** To compare the PK profile of MK-4280 when administered as a co-formulated product with pembrolizumab (MK-4280A, Arm 5, Cohort A) and that when administered sequentially with pembrolizumab (Part B subjects receiving MK-4280 800 mg plus pembrolizumab 200 mg Q3W, Arm 2C) (Cohort A)
- 9) **Objective:** To compare the PK profile of pembrolizumab when administered as a co-formulated product with MK-4280 (MK-4280A, Arm 5, Cohort A) and that when administered sequentially with MK-4280 (Part B subjects receiving MK-4280 800 mg plus pembrolizumab 200 mg Q3W, Arm 2C) (Cohort A)
- 10) **Objective:** To characterize the PK profile of MK-4280 when administered as a co-formulated product with pembrolizumab in subjects in China (MK-4280A, Arm 5, Cohort F)

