## **5.4 Stratification**

No stratification based on age, sex or other characteristics will be used in this trial.

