## **8.2 Responsibility for Analyses/In-House Blinding**

The statistical analysis of the data obtained from this study will be the responsibility of the Clinical Biostatistics department of the Sponsor.

This trial is conducted as an open-label trial, ie, subjects, investigators, and Sponsor personnel will be aware of subject treatment assignments after each subject is enrolled and treatment is assigned.

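### Arm 5 is compared with Arm 2C on safety and PK, but concurrently enrolling 3L+ CRC subjects are allocated by open-label, study-level alternation, so anyone holding the study-wide sequence can know the next arm

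*Combined protocol and SAP*

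**What the plan says.** Section 5.3, repeated in sections 1.0, 7.1.1.7 and 8.1, sets the rule for 3L+ CRC (Cohort A). "If Arms 1, 2C and 5 for 3L+ CRC subjects are enrolling at the same time", then "subjects will be assigned in an alternating fashion across the open arms at the study level through IVRS". No random element or concealment step is described for this allocation. The same section does randomise another cohort: "Randomization for Cohort E in Part B will be performed at a 1:1 ratio by an IVRS/IWRS". Section 5.4 adds: "No stratification based on age, sex or other characteristics will be used in this trial".

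The trial is open-label. Under section 5.2.9, "the Sponsor, investigator and subject will know the treatment administered". Under section 8.2, "Sponsor personnel will be aware of subject treatment assignments after each subject is enrolled and treatment is assigned".

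The Arm 5 versus Arm 2C contrast is planned, not incidental:

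- Primary objective 4 (section 3.1) is to determine the safety of the co-formulation and "compare to the safety and tolerability of MK-4280 and pembrolizumab when administered sequentially", that is, with Arm 2C.
- Secondary objective 8 (section 3.2) reads "To compare the PK profile of MK-4280 when administered as a co-formulated product with pembrolizumab", again against Arm 2C. Objective 9 does the same for pembrolizumab.
- Section 4.2.2.1.4 explains that the Arm 2C subjects were added so that this comparison could be made.
- Section 8.6.1 gives a difference with 95% CI for infusion-related reactions and immune-related AEs, with no adjustment stated.
- Section 8.6.4 gives a 90% CI for the geometric mean ratio from an ANCOVA with body weight and baseline sLAG-3, and allows further covariates.

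Three other provisions bear on the contrast. Arm 5 waits until 10 Arm 2C subjects have completed the DLT period (5.2.2.4). Arm 2C enrolment is not paused while those DLTs are evaluated (5.2.2.2.5). Arm 5 in Cohort A is limited to US sites (5.1.2, 5.2.2.4), and no such limit is stated for Arm 2C.

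**The concern.** In alternation the last assignment fixes the next one. A person who knows the running sequence can decide whether to enter a particular patient now, later or not at all, and so can influence which arm that patient joins. If the patients steered differ in frailty, disease burden or readiness to report events, the arms differ before any treatment is given. Confidence intervals computed as if the two groups were exchangeable do not reflect that.

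The two analyses are not equally exposed. Antibody concentrations are objective measurements and the PK model adjusts for at least two baseline factors. Infusion-reaction and immune-related AE rates depend partly on the investigator's judgement, and they are compared without any stated adjustment.

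**Working it through.** **1. The plan's own precision.** Inputs from section 8.9.4: 40 subjects per arm and SDs on the log scale. Half-width of the 90% CI = t(0.95, 78 df) × SD × √(1/40 + 1/40).

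| Parameter | SD | Computed half-width | Stated |
|---|---|---|---|
| MK-4280 AUC | 0.429 | 0.1597 | 0.159 |
| MK-4280 Cmax | 0.463 | 0.1723 | 0.172 |
| Pembrolizumab AUC | 0.339 | 0.1262 | 0.126 |
| Pembrolizumab Cmax | 0.398 | 0.1481 | 0.148 |

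The figures reproduce to within a unit in the third decimal. The formula assumes two independent, exchangeable groups and makes no allowance for selection.

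**2. How many subjects could be alternated.** All 40 Arm 5 subjects plus the Arm 2C subjects not already needed for the DLT condition: 40 + (40 − 10) = 70 of 80. This is a ceiling. It falls if more than 10 Arm 2C subjects are enrolled before Arm 5 opens, which the unpaused enrolment allows, or if some Arm 2C subjects are at non-US sites, where Arm 5 is not available. It also takes the section 8.1 reading, under which alternation applies when any of the three arms are open together.

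**3. Who can predict the next arm.**

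- Holder of the study-wide sequence, alternation: 100%.
- Site that sees only its own subjects, S equal sites (S is an assumption): it knows the last assignment with probability 1/S and otherwise guesses, giving 1/S + (1 − 1/S)/2 for two open arms. The result is 60%, 55% and 52.5% for S = 5, 10 and 20, against 50% by chance. For three open arms the last term is divided by 3, giving 47%, 40% and 37%, against 33% by chance.
- Holder of the full sequence who also knows the block size, permuted blocks: 71% for fixed blocks of 4 in two arms, 68% for blocks of 6 in two arms, 56% for blocks of 6 in three arms. For blocks of 4, the expected correct guesses are 2.5, 3 and 3 over the three distinct patterns AABB, ABAB and ABBA, so (2.5 + 3 + 3)/3 ÷ 4 = 0.71.
- Simple randomisation: 50% (two arms) or 33% (three arms).

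Blocks therefore reduce predictability but do not bring it to chance for a fully informed observer. That is why block sizes should vary and stay undisclosed.

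**4. What a bias would do if there were one.** The documents give no size, so the spurious ratio r is an assumed range. With SE = SD × √(2/40) and d = ln(r)/SE, coverage of the nominal 90% CI = Φ(1.645 − d) − Φ(−1.645 − d). For MK-4280 AUC, SE = 0.429 × √0.05 = 0.0959. At r = 1.10, d = 0.0953/0.0959 = 0.99 and coverage is 74%.

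| Assumed spurious ratio | MK-4280 AUC | Pembrolizumab AUC |
|---|---|---|
| 1.05 | 86% | 83% |
| 1.10 | 74% | 65% |
| 1.15 | 57% | 42% |

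**5. Precision in a concurrent subset.** With at most 30 Arm 2C and 40 Arm 5 subjects, t(0.95, 68 df) × 0.429 × √(1/30 + 1/40) = 0.173 for MK-4280 AUC, against 0.160 for 40 versus 40.

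**The case against.** The defence has real substance. Alternation runs centrally in a multisite trial, so a site does not normally see the last study-wide assignment, and step 3 shows that its advantage over chance is modest. Section 8.2 says assignments are known after they are made, and nothing in the documents shows the Sponsor choosing or ordering individual Cohort A patients. Arms 2C and 5 deliver the same antibodies at the same doses, so there is little motive to steer between them. This is a Phase 1b trial with openly nonrandom allocation, no hypothesis testing and no acceptance margin for the PK ratio, and its primary endpoint is DLT.

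Most of this limits the point without removing it. Under alternation, knowing past assignments amounts to knowing the next one. The absence of a test does not protect an estimate and its interval. Arm 1 monotherapy is in the same rotation and is the likelier arm to avoid. If the order is fixed, subjects held back from Arm 1 would fall disproportionately on whichever arm follows it, and that may be one of the two compared arms.

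A reader might infer more than the documents support in three places:

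- That every investigator can know the next arm. The mention of regular Sponsor communication in section 5.2.2.2.2 concerns expansion of the Arm 2A cohorts. No section says that sites are sent the running sequence for Arms 1, 2C and 5.
- That the PK model adjusts for weight and sLAG-3 alone. Section 8.6.4 allows further covariates.
- That randomising would cut a holder's predictive ability from 100% to 50%. That figure belongs to simple randomisation, not to permuted blocks.

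**Conclusion.** The weakness stands as a design choice worth changing. During concurrent enrolment, the contrast named in primary objective 4 and secondary objectives 8 and 9 rests on a deterministic sequence in an open-label trial, although the trial's IVRS already randomises elsewhere. It matters most for the unadjusted safety difference in section 8.6.1 and less for the PK ratios.

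It reaches at most 70 of 80 compared subjects, and probably fewer. The documents do not show that selection occurred or would occur, and its size cannot be estimated from them; the coverage figures only illustrate assumed biases. Nor would randomisation make the whole 40 versus 40 contrast randomised. At least 10 Arm 2C subjects precede Arm 5, and any non-US Arm 2C subjects have no concurrent Arm 5 counterpart. The full contrast should be described accordingly.

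**What to change.** In sections 1.0, 5.3, 7.1.1.7 and 8.1, replace alternation with IVRS randomisation at equal allocation among the Cohort A arms open at the subject's site, in permuted blocks of varying, undisclosed size. Naming the arms open at the site also settles a case the present wording leaves unstated: a non-US subject arriving when Arm 5 is next.

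Flag the concurrently randomised US-site subjects in the dataset. In sections 8.6.1 and 8.6.4 add the Arm 5 versus Arm 2C contrast in that subset as a sensitivity analysis, and state that the full 40 versus 40 contrast is not fully randomised.

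If some or all of these subjects have already been allocated, the analysis part still applies: describe the contrast as non-randomised and report it in concurrent US-site subjects.

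The cost is an IVRS list change and wording in the sections named. No subjects, visits or tests are added, and the 40 versus 40 half-widths are unchanged. The subset is slightly less precise, as in step 5 of the working, and more so if fewer than 30 Arm 2C subjects qualify.
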